Patients will be evaluated for safety at scheduled visits until surgery and at the end of study visit approximately 4 weeks after surgery. In addition, after any TG02-treatment the patients will be monitored for heart rate and blood pressure at 5, 10 and 30 minutes and then every 30 minutes thereafter for up to 2 hours post administration.

A FDG PET-CT will be performed before TG02-treatment is initiated (baseline scan should be within the last 4 weeks prior to first TG02-treatment) and a second scan as close as possible before surgery.

Tumour samples for assessment of immune response will be taken pre TG02-treatment in the form of a study specific biopsy and at time of surgery by analysis of the resected tumour tissue. If a pre TG02-treatment biopsy has been taken for diagnostic workup at the hospital, this biopsy, if adequate for the study specific immune analysis and no intervening treatment has been given, can be used as the study specific biopsy if taken within the last 4 week prior to first TG02-treatment. If for any reason the patient does not proceed to surgery, a biopsy will be obtained at the time of planned surgery if possible. In addition, archival biopsy samples from both initial staging (primary diagnosis) and re staging will be utilised, as needed. In the patient information sheet and informed consent form (PIS/ICF), patients will be asked to give consent to the use of archived biopsy material. These archival samples will be used to assess RAS-mutation status and other baseline immune assessments.

Delayed-Type Hypersensitivity (DTH) tests will be performed at week 1, week 4, week 6 and week 8 (if surgery is scheduled for week 8, the DTH test should be performed two days before surgery). If surgery is scheduled for after week 10, and the patient has had only negative DTH tests up to and including week 8, an additional DTH test should be performed at week 10.

Blood samples will be collected for in vitro assessment of TG02-specific immune responses (Immunology sample, PBMC) will be collected at baseline (Day 1, Week 1) and week 8 (Day 64). If surgery is scheduled to occur after week 10, a third sample will be taken as close as possible to the date of surgery.

In total, the study will enrol up to 16 patients for Part I and II.

Subject population: The target population is patients with locally advanced primary and recurrent oncogenic KRAS exon 2 mutant colorectal cancer eligible for radical pelvic surgery at time of enrolment.

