6.2. Study Design

[figure not shown]
The patients with locally advanced primary and recurrent colorectal cancer will be considered for the study. A multi-disciplinary team (MDT) at the sites will coordinate the staging and work up of the patients and select appropriate patients for curative surgery. Selected patients for surgery will either receive chemo-radiation treatment (3-5 weeks) or have no further treatment before they are being consented for the study, see patient flow and timelines in [Figure 1](#).

Figure 1: Patient flow and timelines

Patient flowchart with pre-surgery chemo/radiation

Patient flowchart without pre-surgery chemo/radiation

[figure not shown]
The patient will be defined as on study from the date of signed informed consent until the end of study (EOS) visit which should be scheduled after surgery.

The study is divided into two parts, Part I followed by Part II if decision of such will be made by the sponsor. Part II may start when all safety data, systemic immune responses (Delayed-Type Hypersensitivity (DTHs)) and tumour material (analysed for intra-tumoural T cell infiltration) are available for 4-6 patients in Part I of the study. The sponsor, after input from the Steering Committee, will evaluate the data to assess safety and preliminary immune activity and efficacy of TG02-treatment, and make a recommendation to proceed or not to Part II of this protocol.

Patients from Part I will not participate in Part II.

[figure not shown]
The study design for Part I is shown in [Figure 2](#) and the study design for Part II in [Figure 3](#).

Figure 2: Study design graphics Part I

- 1: Core needle biopsy pre TG02-treatment.
- 2: Tumour tissue at resection, at time of surgery.
- 3: If no surgery before week 10, a TG02-treatment will be given.
- 4: Only to be taken for patients who have surgery at week 10 or later and had a negative DTH outcome at week 8.
- 5: If surgery is after week 10, a sample will be taken as close as possible to surgery.

Figure 3: Study design graphics Part II

- 1: Core needle biopsy pre TG02-treatment.
- 2: Tumour tissue at resection, at time of surgery.
- 3: If no surgery before week 10, a TG02-treatment will be given.
- 4: Only to be taken for patients who have surgery at week 10 or later and had a negative DTH outcome at week 8.
- 5: If surgery is after week 10, a sample will be taken as close as possible to surgery.

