The treatment period will be from Day 1 (Week 1) and up to surgery, which is planned for week 8 but can occur in a window up to week 14. The following assessments will be performed on Day 1, Day 8, Day 15, Day 22, Day 36, Day 50 and if surgery is after week 10 (Day 64):

- Vital signs (heart rate, blood pressure and tympanic body temperature) and ECOG performance status
- Concomitant medications and adverse events will be monitored continuously
- Physical examination, haematology and serum biochemistry (Table 9-1) before treatment (Day 1) and during treatment on Day 15, Day 36, Day 50 and if surgery after week 10 (Day 64).
- TG02 treatment will be administered on Days 1, 8, 15, 22 and 36. If surgery after week 10 TG02 treatment will also be given at week 10 (Day 64).
- Pembrolizumab will be given on Days 22 and 36. If surgery is scheduled after Day 50/Week 8, pembrolizumab will be given at Day 50/Week 8. If surgery scheduled after Day 64/Week 10, a further pembrolizumab infusion will be given at Day 64/Week 10.
- DTH tests will be performed at baseline (Day 1), week 4 (Day 22), week 6 (Day 36) and week 8 (Day 50) (if surgery is scheduled for week 8 the DTH test should be performed two days before surgery). If surgery is after week 10, and the patient has had negative DTH tests up to and including week 8, an additional DTH test should be performed at week 10 (Day 64).

- Blood samples for in vitro assessment of TG02-specific immune responses (Immunology sample, PBMC) will be taken at baseline (Day 1) and Day 50. If surgery is after week 10, an additional sample should be taken as close as possible up to the date of surgery (see separate Immune monitoring plan).
- The CEA biomarker will be evaluated at Day 50. If surgery is after week 10 a third sample will be taken at Day 64 or just prior to surgery, whichever is the more appropriate.
- Tumour samples for assessment of immune response will be taken at time of surgery. If for any reason the patient will not have surgery a biopsy will be obtained if possible at the latest by week 14 (see separate Immune monitoring plan).
- FDG PET-CT scan for tumour assessment of standard uptake value (SUV-max) as close as possible up to date of surgery.
- Circulating Tumour Cells (CTC) will be evaluated at Day 1 and Day 50. If surgery is after week 10, an additional sample can be taken as close as possible up to the date of surgery.

Additional monitoring during the first 2 hours after any TG02-treatment:

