- d: Tumour tissue taken during resection. If for any reason, the patient will not have surgery a biopsy will be obtained if possible.
- e: To be done 2-0 days before surgery
- f: If surgery is scheduled for week 10, there will be no TG02-treatment given at week 10. If no surgery at week 10, the last TG02-treatment to be given at week 10.
- g: As close as possible up to the date of surgery.
- h: At the visits when TG02 and/or TG02-treatment (and pembrolizumab in Part II) is scheduled, the assessments should be performed prior to the treatments.
- i: Only to be taken for patients who have surgery after week 10 and had a negative DTH outcome at week 8. DTH (TG02) injection to be done 48 hours prior to surgery.
- j: Assessment of DTH (TG02) injection site to be done 48 hours (+/- 4 hours) after each DTH (TG02) injections by the patient in a study specific diary.
- k: Only applicable in Part II of the protocol
- l: To be done prior to surgery
- m: Allowed time for surgery (resection specimen) scheduled for week 8 is + 2 week and allowed time for surgery (resection specimen) scheduled for week 10 is + 4 week
- n: Blood samples for routine haematology and serum biochemistry to be recorded if already available in the patient medical record (standard of care)
- o: End of study visits to be scheduled during the hospitalized post-operative recovering period, up to 6 weeks after surgery.
- p: TG02-treatment is a combination of the two IMPs: GM-CSF and TG02. When TG02-treatment is administered, GM-CSF is to be given as an intradermal injection 15-30 minutes before the TG02 intradermal injection. GM-CSF and TG02 are administered as 2 separate intradermal injections, 15 to 30 minutes apart, at the same site in the upper arm. After any TG02-treatment the patients will be monitored for heart rate and blood pressure at 5, 10 and 30 minutes and then every 30 minutes thereafter for up to 2 hours post administration
- q: In addition, TG02 will, at certain time points, be administered intradermally (without prior administration of GM-CSF) in the lower area of the contra lateral arm as DTH test. The administration of GM-CSF (0.10 mL reconstituted GM-CSF) and TG02 (0.10 mL reconstituted TG02) has to be strictly intradermal.
- r: Should be within the last 4 weeks prior to first TG02-treatment.
- s: If surgery is scheduled after Day 50/Week 8, pembrolizumab will be given at Day 50/Week 8.

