9. STUDY ASSESSMENTS

9.1. Assessment of Efficacy

9.1.1. Primary Efficacy Variables

A systemic immune response is defined as having a positive in vivo DTH and/or a positive in vitro T-cell response at least once during the treatment period. Change intra-tumoural T-cells in resected tumour tissue at surgery compared to pre TG02-treatment core biopsy will be investigated.

Delayed Type Hypersensitivity (DTH)

DTH tests are performed in order to demonstrate whether a TG02 RAS mutation specific immune response has been elicited.

[figure not shown]
Administration of TG02 only (without GM-CSF or preceded by TG02-treatment) must be injected intradermally in the lower area of the contralateral arm to TG02-treatment as a Delayed Type Hypersensitivity (DTH) test.

The DTH test is administered at baseline (Day 1 before treatment) week 4, week 6 and week 10 if surgery is scheduled after week 10 and the patient has not shown positive DTH reaction.

The DTH skin reaction assessment is to be performed 48 hours (+/- 4 hours) after each administration by the patient in a study specific diary. The patient will be instructed by the study nurse how to record the DTH response and how to enter the results into the diary. The DTH-test will be considered positive if the area of the skin reaction has an average diameter* of ≥ 5 mm at the 48 hours (+/- 4 hours) assessment ([Figure 4](#)).

Figure 4: DTH Skin Reaction Registration (induration and erythema)

* Average diameter: $\frac{a \text{ mm} + b \text{ mm}}{2}$

T-cell Analyses

Immunology-processed blood samples (PBMC) will be taken at baseline (Day 1, Week 1) and week 8 (Day 50). If surgery is after week 10, a third sample will be taken as close as possible up to the date of surgery. All samples will be processed and stored under appropriate conditions until being analysed in batches to minimize day to day assay variability. PBMCs will be analysed for the presence of TG02 specific T-cells which will be described in a study specific Immune Monitoring Plan.

Tumour biopsy assessment

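### The DTH section of the protocol leaves out the week 8 test, and the conditional week 10 test has conflicting entry and timing rules, some of which can change who counts as a DTH responder

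*Protocol*

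**What the plan says.** **Weeks tested.** Protocol 9.1.1 gives the schedule as "The DTH test is administered at baseline (Day 1 before treatment) week 4, week 6 and week 10", the last of these "if surgery is scheduled after week 10 and the patient has not shown positive DTH reaction". It does not list week 8. The synopsis says "Delayed-Type Hypersensitivity (DTH) tests will be performed at week 1, week 4, week 6 and week 8". Sections 4.8, 6.4.2 and 8.2 and Tables 6-1 and 8-1 also include week 8.

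**Week 10, by surgery date.** The synopsis, 6.4.2, 9.1.1, Table 6-1 footnote i and the Table 8-1 row label require surgery after week 10. Note 4 to Figures 2 and 3 reads "Only to be taken for patients who have surgery at week 10 or later and had a negative DTH outcome at week 8", and the Table 8-1 footnote sets the same condition against its own row label. Table 6-1 places the test in the column for surgery at week 10 (Day 64), although its footnote i says "Only to be taken for patients who have surgery after week 10 and had a negative DTH outcome at week 8".

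**Week 10, by earlier result.** The synopsis requires that "the patient has had only negative DTH tests up to and including week 8". Section 6.4.2 agrees, and 9.1.1 has the equivalent condition of no positive reaction so far. The figure notes, Table 6-1 footnote i and the Table 8-1 footnote look only at the week 8 result.

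**Week 10, timing.** Section 6.4.2 puts the test on Day 64, and 8.2 puts a DTH dose 30 minutes before the TG02-treatment. Table 6-1 footnote i puts it 48 hours before surgery, which may be as late as Day 92.

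**Responder.** Protocol 11.6.1.2 and SAP 6.1.1 both count any patient with at least one positive DTH test at any time in the study. The SAP lists no qualifying time points. Its section 3.3 refers to protocol Table 6-1.

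**The concern.** With an any-positive definition, the set of tests offered is part of the endpoint. If sites can read the schedule in different ways, two patients with the same biology may be classified differently because one was tested on an occasion when the other was not, or was tested after one more TG02-treatment.

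The endpoint is primary, and the synopsis and sections 6.2 and 13.5 make DTH one of the inputs to the decision on Part II. Numbers are small: one reclassified patient moves the Part I rate by 1/6 = 17 to 1/4 = 25 percentage points, and the Part II rate by 1/10 = 10 points if ten are enrolled.

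Two further consequences follow in the SAP. By-time-point percentages use patients with data at that visit (SAP 6.4.2), so the week 10 denominator depends on the entry rule applied. Assessment outside the time window is a deviation category (SAP 4.4), and major deviations remove a patient from the per protocol set (SAP 4.2). With conflicting schedules it is unclear which tests are out of window.

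**Working it through.** The documents give no power, alpha or assumed response rate, so there is no stated figure to reproduce. The check has four steps.

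**1. Number of tests.** Inputs: the DTH days above, with week 10 taken as Day 64 as in Table 6-1. Post-baseline tests for a patient with no earlier positive:

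| Surgery | 9.1.1 read literally | Week 8 included, surgery after week 10 | Week 8 included, surgery at week 10 or later |
|---|---|---|---|
| Day 50 to 63 | 2 | 3 | 3 |
| Day 64 | 2 | 3 | 4 |
| Day 65 to 92 | 3 | 4 | 4 |

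A count of 2 arises only in the first column. Otherwise the count is 3 or 4. It depends on the wording only for surgery at week 10 itself; elsewhere it follows from the surgery date.

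**2. Which conflicts can change responder status.**

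- *Week 8 omission:* yes, for a patient whose first positive would be at week 8. Of the 2^4 = 16 result patterns over Days 1, 22, 36 and 50, one (negative, negative, negative, positive) changes status.
- *At versus after week 10:* yes, for surgery on Day 64 with all earlier tests negative, because one rule gives a further test and the other does not.
- *All negative versus week 8 negative:* no. The rules disagree on who is tested in 8 − 1 = 7 of the 16 earlier patterns (8 have week 8 negative, 1 has all negative). In each of those 7 there is already a positive, so any-positive status differs in 0 of the 32 patterns that include a week 10 result.
- *Timing:* yes, through what is measured; see step 3.

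**3. Timing.** Surgery on Day 65 to 92 less 2 days gives a test on Day 63 to 90. This equals Day 64 only when surgery is on Day 66 (66 − 2 = 64). TG02-treatment is given on Days 1, 8, 15, 22 and 36, and again on Day 64 when surgery is after week 10 (6.4.2). A Day 64 test given before that day's treatment follows five treatments. A test 48 hours before surgery falls on Day 63, still after five, if surgery is on Day 65. It falls on Day 65 to 90, after six, if surgery is on Day 67 to 92.

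**4. Size of one additional test.** The per-test positivity p is an assumption; the documents give none. With independent tests, the any-positive rate is 1 − (1 − p)^k:

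| p | k = 3 | k = 4 | Difference |
|---|---|---|---|
| 5% | 1 − 0.95^3 = 14.3% | 1 − 0.95^4 = 18.5% | 4.3 points |
| 10% | 1 − 0.90^3 = 27.1% | 1 − 0.90^4 = 34.4% | 7.3 points |
| 20% | 1 − 0.80^3 = 48.8% | 1 − 0.80^4 = 59.0% | 10.2 points |

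(Differences are taken before rounding.) Repeat tests in one patient are likely to be positively correlated, which shrinks these gaps; with perfect correlation they are zero.

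**The case against.** The strongest reply is that the week 8 omission looks like an isolated drafting slip. All the other schedules have the test, and the SAP takes its visits from Table 6-1, so a site would have to follow one sentence against both schedule tables to skip it. That largely stands, and the range of 2 to 4 tests should not be presented as what the plan will produce. The reply does not settle week 10, because Table 6-1 disagrees with its own footnote on surgery date, and that footnote disagrees with 6.4.2 on timing.

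It is also fair that most of the difference between 3 and 4 tests is intended. It comes from a surgery window of week 8 to week 14 and will remain after the text is reconciled. The study is descriptive with no hypothesis, and DTH testing is meant to be the same in both parts, so no type I error rate is at stake and the wording favours neither part. SAP 6.1.1 already gives results by time point and lists all DTH data, so a careful reader could reconstruct response through week 8.

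A reader might infer three stronger things that the documents do not support:

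- That a patient positive at week 4 and negative at week 8 is exposed to misclassification. That patient is already a responder under either rule.
- That the rise from 11 to 16 DTH responders in protocol 4.7 shows the effect of testing more often. It followed two additional vaccine administrations, so it shows that first positives can appear late and does not isolate repeat testing.
- That the response rate is inflated by a known amount. The rates in the working rest on assumed positivity and independence.

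**Conclusion.** The inconsistencies are real and touch a primary endpoint. Three of them can change responder status: the week 8 omission if 9.1.1 is followed literally, at versus after week 10 for surgery on Day 64, and Day 64 versus 48 hours before surgery. The fourth, on earlier results, affects only who receives another test and the week 10 by-time-point counts.

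The expected size is modest: one test more or fewer for a minority of surgery dates, worth about 4 to 10 percentage points in the any-positive rate for p between 5% and 20% under independence, and less with positive correlation. The harm is to interpreting the response rate and to comparing Part I with Part II. The correction is worth making because it fixes how a primary endpoint is ascertained and costs almost nothing.

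**What to change.** **Protocol.** Reconcile 9.1.1, the synopsis, 6.4.2, the notes to Figures 2 and 3, Table 6-1 with footnote i, and Table 8-1 with its footnote, so that there is one list of DTH weeks, one week 10 entry rule (surgery date and earlier results) and one week 10 timing. Which rule is right is for the sponsor and investigators; this review does not choose.

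**SAP 6.1.1.** Name the time points that count towards response. Report, for Part I and Part II, the post-baseline DTH response through week 8 beside the any-time response. If week 8 stays in the reconciled list, the first figure uses only tests scheduled for all patients. Exclude the Day 1 pre-treatment test from it; the present any-time definition would count a positive on that day.

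**Cost.** Wording edits and one additional table row. No new data are needed. Protocol 4.2 reports that four people have already received TG02, so for patients already tested the wording change comes too late, and the SAP row is the part that helps.

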9.1.2. Secondary Efficacy Variables

Tumour biopsy assessment

The same processing procedure as described for primary efficacy variables will be followed.

Immunohistochemical staining will be performed to investigate; pathological responses and markers of apoptosis (such as activated Caspase 3, granzyme B), immune cell subsets (such as T effector cells, B cells, NK cells, T-regs, MDSC), and PD-L1 expression on epithelial cells in baseline biopsies and resected tumour tissue at surgery.

The collection, storage, parameters and analyses to be used will be described in a study specific Immune Monitoring Plan.

FDG PET/CT assessment

FDG uptake reflects the tumour activity independent of the morphologic characteristics. Sequential FDG-PET/CT can provide vital information in monitoring treatment response in tumour.

FDG PET/CT images will be performed at screening (should be within the last 4 weeks prior to first TG02-treatment), and as close as possible up to the date of surgery. The scans will be captured according to the site's standard imaging procedure. Standard uptake value (SUV) will be measured at baseline and post treatment will be assessed.

The images will be anonymized and provided with a unique study identification number, one for the Investigators file and one for the Sponsor file

Changes in Tumour Marker CEA

Tumour marker assessment will be done to follow the evolution of the disease under treatment. The marker of choice will be CEA. This marker will be evaluated at screening, week 8 and if surgery is after week 10, a sample will be taken as close as possible to surgery.

The analysis of this marker will be performed locally at each site according to local procedures.

9.1.3. Exploratory Efficacy Variables

Changes in circulating tumour cells and/or circulating tumour DNA

Change in circulating tumour cells (CTC) will be measured to follow the evolution of levels of CTC during the treatment period. The Investigators will arrange to have the plasma sample transported directly to the central laboratory for analyses according to the procedures detailed in a laboratory manual.

Functionality of RAS mutation specific T cells in tumour tissue and peripheral blood

Cytotoxic functionality of RAS mutation specific T cells grown from fresh tumour tissue or PBMC will be studied as described in the study specific Immune Monitoring Plan.

9.2. Assessment of Safety

9.2.1. Adverse Events

It is important that all the staff involved in the trial is familiar with the content of this section of the protocol.

9.2.1.1. Definitions

An adverse event (AE) is the development of an undesirable medical condition or the deterioration of a pre-existing medical condition in a patient under clinical investigation who has been administered an investigational pharmaceutical product (in this case GM-CSF/TG02 but which does not necessarily have a causal relationship with this treatment. An undesirable medical condition can be symptoms (e.g., nausea, chest pain) signs (e.g., tachycardia, enlarged liver) or abnormal results of an investigation (e.g., laboratory findings, ECG). An AE can include any undesirable condition occurring at any time after inclusion in the study, even if no trial treatment has been administered or recently administered. A grading severity scale is provided for each AE term. NCI Criteria for Adverse Events (CTCAE) (v4.03: June 14, 2010) includes five grades (1-5), with grade 5 being death.

Any events that are unequivocally due to disease recurrence must not be reported as AEs.

A serious AE (SAE) is an event that is known with certainty, or suspected with good reason, to constitute a threat to life or to cause severe or permanent damage. A SAE can occur during any phase of the trial and at any dose of the investigational product. This is particularly true for an AE that:

- results in death
- is immediately life-threatening
- requires patient hospitalisation or prolongation of existing hospitalization
- results in persistent or significant disability/incapacity or
- is a congenital anomaly/birth defect
- is an important medical event that may have jeopardised the patient or may have required medical intervention to prevent one of the outcomes listed above.

Medical and scientific judgment is to be exercised in deciding on the seriousness of a case. Important medical events may not be immediately life-threatening or result in death or hospitalisation, but may jeopardise the patient or may require intervention to prevent one of the listed outcomes in the definitions above. In such situations, or in doubtful cases, the case should be considered as serious. Drug misuse and drug overdose and should be regarded as serious, even if they may not result in the above mentioned outcomes.

Hospitalisation for administrative reason (for observation or social reasons) is allowed at the investigator's discretion and will not qualify as serious unless there is an associated adverse event warranting hospitalisation (see [Appendix I](#) and [Appendix II](#) for additional safety information).

The causality of AE/SAEs (i.e., their relationship to trial treatment) will be assessed by the individual investigators at each trial centre who must while completing the CRF answer yes/ no to the question 'do you consider that there is a reasonable possibility that the AE/SAE may have been caused by the investigational drug?'

Any events that are unequivocally due to disease recurrence must not be reported as AEs.

The specialist group handling the pharmacovigilance for the study is:

[REDACTED]

The [REDACTED] is specialised and has the appropriate expertise in handling and reporting SAEs.

9.2.1.2. *Adverse Event Reporting*

For the purpose of this trial, any detrimental change in a patient's condition, subsequent to their entry into the trial and during the 28-day follow-up period after the final treatment, should be considered an AE.

The development of a new cancer should be regarded as an AE. New cancers are those that are not the primary reason for the administration of the trial treatment and have been identified after the patient's inclusion into this clinical trial.

Any events that are unequivocally due to disease recurrence must not be reported as AEs.

If the same AE occurs at several investigation times in one patient, then the AE in question must be documented and assessed as new each time.

All AEs are to be recorded on the CRFs provided and Serious Adverse Events also on the Serious Adverse Event Form. A description of the event, including its severity, duration, any action taken (e.g. treatment and follow-up tests) and the outcome is to be provided, along with the investigator's assessment of the relationship to the trial treatment. AEs and laboratory values will be graded according to the NCI Criteria for Adverse Events (CTCAE) (v4.03: June 14, 2010) and recorded on the appropriate CRF page.

The reporting of laboratory/vital signs abnormalities as both laboratory findings and adverse events should be avoided. They should not be reported as AEs unless any criterion of clinical significance and/or a SAE is fulfilled, the laboratory/vital signs abnormalities cause study drug dose adjustment, lead to patient discontinuation of their trial treatment, or the investigator insists that the abnormality is reported as an AE. If an abnormal laboratory

value/vital sign is associated with clinical signs and symptoms, the sign/symptom should be reported as an AE and the associated laboratory result/vital sign should be considered additional information that must be collected on the relevant CRF.

All patients who have new or worsening NCI-CTC grade 3 or 4 laboratory values at the time of withdrawal must have further tests performed and the results recorded on the appropriate CRF, until the laboratory values have returned to NCI-CTC grade 1 or 2, unless these values are not likely to improve because of the underlying disease. In these cases, the investigators must record their opinions on the CRFs and in the patients' medical records. For an AE to be a suspected drug-related event there should be at least a reasonable possibility of a causal relationship between the trial medicinal product and the AE (see [Appendix II](#) for guidelines on interpretation of causality).

It is important to distinguish between serious and severe AEs. Severity is a measure of intensity whereas seriousness is defined by the criteria in [section 9.2](#). An AE of severe intensity need not necessarily be considered serious. For example, nausea that persists for several hours may be considered severe nausea, but is not an SAE. On the other hand, a stroke that results in only a limited degree of disability may be considered a mild stroke, but would be an SAE.

Lack of efficacy

When there is deterioration in the condition for which the medicine is being used there may be uncertainty as to whether this is lack of efficacy or an AE. In such cases, unless Targovax or the reporting physician considers that the medicine contributed to the deterioration or local regulations state to the contrary, **the deterioration should be considered to be a lack of efficacy and not an AE.**

Handling unresolved SAEs/AEs at completion/withdrawal

All trial treatment-related toxicities and SAEs must be followed until resolution unless, in the investigator's opinion, the condition is unlikely to resolve because of the patient's underlying disease.

Procedure for reporting serious adverse events

Investigators and other site personnel must inform the study monitor of any SAE that occurs in the course of the study as soon as possible but definitely within 24 hours of when he or she becomes aware of it.

The following minimal information must be faxed immediately to [contact]

- Patient identifier – patient number, investigator
- Details of the event or outcome (see [section 9.2](#))

To discuss the medical aspects of the SAE investigators should call:

██

This number should also be called to report a life-threatening or fatal adverse event within 2 hours of knowledge of the event if this occurs before recognised recurrence of disease.

The dedicated email address for SAE information is:

██

The SAE must be documented in the patient's medical source documents and the outcome described.

The monitor will work with the investigator to compile all the necessary information and ensure that the appropriate Drug Safety Department receives a report within 24 hours for all fatal and life-threatening cases and by day 5 for all other SAEs.

Follow-up information on SAEs must also be reported by the investigator within the same time frames.

If a non-serious AE becomes serious, this and other relevant follow-up information must also be provided to safety group within 24 hours as described above.

All SAEs have to be reported, whether or not considered causally related to the investigational product. All SAEs will be recorded in the CRF. The investigator is responsible for informing the Ethics Committee and/or the Regulatory Authority of the SAE as per local requirements.

Additional information will be requested, if necessary, by the Trial Physician within 5 days of the receipt of the SAE report. This is to ensure that the initial reporting of SAEs is made to the regulatory authorities within the required time-frame. All withdrawals from trial treatment must be notified to the trial physician. Withdrawals from treatment due to a new, previously unreported SAE must be notified to the Trial Physician, along with the SAE. Withdrawal from trial treatment for a previously reported SAE can be made within the 7 days after the decision has been made to withdraw the patient and for a non-serious AE within 21 days of the decision to withdraw. After withdrawal from treatment patients must be followed up for AEs for 28 days after the last dose of trial medication. All SAEs recorded during that period must be reported to the safety group, and followed up until resolved unless in the Investigator's opinion the condition is unlikely to resolve due to the patient's underlying progressive disease.

